### **IRRs**

- MedDRA Hypersensitivity SMQ broad selection
- MedDRA Anaphylactic reaction SMQ broad selection
- MedDRA Extravasation events (injections, infusions and implants) SMQ broad selection, excluding implants and occurs within 48 hours of an infusion/injection, or within 2 days if the AE start time is not available.

In case of partially missing AE start date, the AE will be considered an IRR, unless the available parts of the AE start date provide evidence it did not occur within 48 hours of an infusion/injection.

**Infusion related reactions (IRRs)** are defined as all AEs with a MedDRA PT that is listed in either:

The event rate per 100 PYFU is defined as 100 \* the number of events divided by the sum of the follow-up time during which an event is considered treatment-emergent of all participants per treatment arm expressed in years (i.e. divided by 365.25).

All AEs, including pretreatment events will be listed.

### 14.1.1. All TEAEs

Summary tables will only include TEAEs and will be presented by System Organ Class (SOC) and Preferred Term (PT) for each treatment regimen and total. Table will contain number and percentage of participants with at least one event and the number of events (except for TEAEs by worst toxicity) for TEAE. These outputs will be provided for:

**TEAEs** 

Document: BIOSdata\argenx\Efgartigimod\HAB40220\Biostatistics\Documentation\SAP

Author: 1.0 Version Number:

> Version Date: 03 June 2024

Template No.: CS\_TP\_BS016 Revision 7 Reference: CS\_WI\_BS005

Page 32 of 54

- Serious TEAEs
- Nonserious TEAEs
- Grade ≥3 TEAEs

TEAEs by worst toxicity (FPA Only)

- Treatment-related TEAEs
- Procedure-related TEAEs
- Serious treatment-related TEAEs
- TEAEs leading to IMP discontinuation or interruption.
- TEAEs of special interest by worst outcome
- IRRs
- Serious IRR (IA and FPA)

## 14.2. Laboratory Evaluations

Results from the central laboratory will be included in the reporting of this study for serum chemistry and hematology, coagulation, urinalysis, serology (eg, viral marker testing), and specialty laboratory parameters. A list of laboratory assessments to be included in the outputs is included in Appendix 2 (Table 2) of the protocol. These are mainly as follows.

### **Laboratory Assessments**

Hematology	RBC count, platelet count, hemoglobin, hematocrit, RBC indices: MCV, MCH, %reticulocytes WBC count with differential: neutrophils, eosinophils, lymphocytes, basophils, monocytes		
Serum chemistry	ALT, AST, albumin a , blood urea nitrogen, creatinine, glucose, potassium, chloride bicarbonate, sodium, total protein a , calcium, bilirubin (total and direct)		
Routine urinalysis	Specific gravity, pH, glucose, protein, blood, ketones, bilirubin, urobilinogen, nitrite, leukocyte esterase, microscopic examination (if blood or protein is abnormal)		
Pregnancy testing	Urine test (as needed for WOCBP potential, defined in Section 10.4.1 of the protocol)		
Specialty laboratory tests:	CRP, ESR, TSH		

Document: BIOSdata\argenx\Efgartigimod\HAB40220\Biostatistics\Documentation\SAP

Author: Version Number: 1.0

Version Date: 03 June 2024

Template No.: CS\_TP\_BS016 Revision 7 Reference: CS\_WI\_BS005

Page 33 of 54

ALT=alanine aminotransferase; AST=aspartate aminotransferase; BUN=blood urea nitrogen; CRP=Creactive protein; ESR=erythrocyte sedimentation rate; MCH=mean corpuscular hemoglobin; MCV=mean corpuscular volume; RBC=red blood cell; TSH=thyroid stimulating hormone; WBC=white blood cell; WOCBP=women of childbearing potential

a Results will be blinded up to and including the date of database lock on 2104, so as not to unblind 2104 prematurely.

Normal ranges are available as provided by the central laboratory and results will be presented in standardized units unless specified otherwise. Clinically significant changes occurring during the study are recorded as an AE.

Quantitative laboratory measurements reported as "< X", i.e. BLQ, or "> X", i.e. above the upper limit of quantification (ULQ), will be converted to X for the purpose of descriptive summaries, but will be presented as recorded, i.e. as "< X" or "> X" in the listings. For Toxicity grades the <X and >X will be represented within the

Continuous laboratory parameters will be summarized using descriptive statistics of actual values and changes from baseline at each analysis visit. Categorical parameters will only be listed.

The following summaries will be provided for laboratory data:

- Continuous laboratory parameters to be summarized using descriptive statistics of actual values and changes from baseline at each analysis visit for SAF at the IA and FPA.
- Laboratory toxicity grades to be presented as cross-tabulations of the toxicity at each postbaseline analysis visit and at the worst-case analysis visit versus the baseline toxicity for SAF at the IA and FPA.
- Laboratory abnormalities as cross-tabulations of the abnormality at each postbaseline analysis visit and at the worst-case analysis visit versus the baseline abnormality for SAF at the IA and FPA.
- The number of participants with treatment-emergent abnormalities will also be shown. The denominator for the percentage is the total number of participants per treatment arm and per analysis visit in the SAF.
- Listing of participants with any post-baseline abnormality or toxicity grade  $\geq 1$ .

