# 3. OBJECTIVES, ENDPOINTS, AND ESTIMANDS

Table 3: Study ARGX-113-2105 Objectives and Endpoints

Objectives	Endpoints
Primary	
Evaluate the long-term safety of efgartigimod in patients with PC-POTS	Incidence and severity of AEs and AESIs, incidence of SAEs, changes in clinically significant laboratory test results (per investigator judgment), vital signs, and ECG results
Secondary	

 
Evaluate the long-term efficacy of efgartigimod in reducing the severity of PC-POTS symptoms
 
	
 
Change from baseline to week 24 and week 48 in COMPASS 31 (modified)
 
Change from baseline to week 24 and week 48 in MaPS
 

Evaluate the long-term efficacy of efgartigimod on patient global assessment of symptom experience, fatigue, and cognitive function	
 
Change from baseline to week 24 and week 48 in PGI-S
 
PGI-C at week 24 and week 48
 
Change from baseline to week 24 and 48 in the PROMIS Fatigue Short Form 8a
 
Change from baseline to week 24 and 48 in the PROMIS Cognitive Function Short Form 6a
 

Assess the PD effect of efgartigimod	Absolute values, changes from baseline, and percent reduction from baseline in total IgG levels over the 48-week treatment period
Assess the exposure to efgartigimod	Efgartigimod serum trough concentrations over the 48-week treatment period
Assess the immunogenicity of efgartigimod	Incidence and prevalence of ADA against efgartigimod over the 48-week treatment period
Exploratory	

ADA=antidrug antibodies; AE=adverse event; AESI=adverse events of special interest; COMPASS=Composite Autonomic Symptom Score; ECG=electrocardiogram;

IgG=immunoglobulin G; MaPS=Malmö POTS Symptom Score; PC-POTS=post-COVID-19 postural orthostatic tachycardia syndrome; PD=pharmacodynamic; PGI-C=Patient Global Impression of Change; PGI-S=Patient Global Impression of Severity; PROMIS=Patient-Reported Outcomes Measurement Information System; SAE=serious adverse event

No estimands have been defined for this study.

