# 9.3. Statistical Analyses

#### 9.3.1. General Considerations

The results of this study will not be used inferentially. No formal sample size calculation is presented.

Summaries will include the number of observations (n), mean, SE, 95% CI, median, minimum, and maximum for continuous measures. Summaries will include sample size, frequencies, and percentages for categorical variables. For categorical variables, participants with missing data will be counted as a separate category; proportions will be calculated using as denominator all enrolled participants.

All study visits will be recalculated based on actual dates. The rules for calculating the analysis visits and for imputing partial dates or missing dates will be documented in the SAP.

Summaries will be provided both for the overall study population as well as grouped according to treatment received in Study ARGX-113-2104 (efgartigimod or placebo).

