## 9.3.2. Primary Endpoint Analysis

The primary endpoint is the incidence and severity of AEs and AESIs, incidence of SAEs, changes in laboratory test results, vital signs, and ECG results.

AEs will be coded using the latest version of the MedDRA classification system.

All AEs starting on or after the first infusion will be categorized as TEAEs.

TEAEs will be presented by SOC and PT, and will include the percentage of participants reporting at least one TEAE by SOC and PT and overall.

Multiple occurrences of a single PT in a participant will be counted only once at the maximum severity/grade.

The number and percentage of participants with most common AEs will be presented.

AEs with missing severity or relationship to IMP will be classified as severe and treatment-related, respectively. All AEs will be summarized by relatedness to IMP.

Any AEs leading to death or discontinuation of IMP will also be summarized.

All AE data will be listed.

The other safety endpoints will be summarized using descriptive statistics.

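### SAP 14.2 gives qualitative urinalysis results no count or shift unless they are recorded as AEs or classified High/Low/Normal, which does not match the protocol's summary rules

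*SAP*

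**What the plan says.** SAP 14.2 (Laboratory Assessments) provides descriptive statistics of values and changes from baseline for continuous parameters. For the rest it says "Categorical parameters will only be listed". The same section plans "Laboratory abnormalities as cross-tabulations of the abnormality at each postbaseline analysis visit and at the worst-case analysis visit versus the baseline abnormality", and SAP 14.2.1 extends that table to protocol parameters that are outside Appendix 2 but have a High/Low/Normal classification.

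The protocol is more general. Section 9.3.1 says "Summaries will include sample size, frequencies, and percentages for categorical variables". Section 9.3.2, after dealing with AEs, says "The other safety endpoints will be summarized using descriptive statistics".

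The urinalysis panel is given in SAP 14.2 as "Specific gravity, pH, glucose, protein, blood, ketones, bilirubin, urobilinogen, nitrite, leukocyte esterase", with microscopy if blood or protein is abnormal. The protocol's Schedule of Activities places urinalysis at baseline and weeks 12, 24 and 48.

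**The concern.** A listing is not a descriptive summary. For categorical laboratory parameters the SAP therefore does less than Protocol 9.3.1 and 9.3.2 describe. The visible text under SAP 3.4, where changes from the protocol belong, concerns only the baseline definition.

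The SAP is also uneven within itself. Continuous laboratory values are tabulated in full, whether or not an investigator thought any of them clinically significant. Qualitative values get no such table. A laboratory summary is meant to show a modest shift across participants that nobody flagged one patient at a time. With about 38 participants followed for close to a year, such a shift in a dipstick parameter would have to be found by reading a listing.

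**Working it through.** The plan gives no figure to reproduce on this point. The check is to follow a urinalysis result through every route in the SAP that could lead to a count, and then to size what is left.

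**Route 1: adverse events.** SAP 14.2 says "Clinically significant changes occurring during the study are recorded as an AE". Protocol 8.3.4 says the same, and Protocol 10.3.1 names urinalysis among the tests whose clinically significant abnormalities are collected as AEs. Treatment-emergent AEs are then tabulated by number and percentage (SAP 14.1). A result that the investigator judges clinically significant is therefore counted. A result not so judged is not. Under Protocol 8.3.4, findings associated with the underlying disease do not qualify unless more severe than expected.

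**Route 2: toxicity grades.** SAP 14.2.1 grades only Appendix 2 parameters. Appendix 2 contains no urinalysis parameter, so this route is closed to all of them.

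**Route 3: abnormality cross-tabulation.** SAP 14.2.1 admits protocol parameters with High/Low/Normal, so lack of an Appendix 2 row does not exclude a parameter here. Low, Normal and High are each defined by comparing a value with normal-range limits. Numeric items with a range, such as pH and specific gravity, can enter. The section defines no negative/positive or normal/abnormal category, so a purely qualitative result has no stated place.

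**Route 4: listing.** This is all that remains for a qualitative result that took neither route 1 nor route 3. SAP 14.2 also lists participants with any post-baseline abnormality, but abnormality is not defined for a qualitative result.

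**Scale.** Inputs:
- expected participants: about 38 (Protocol 9.5; SAP 3.2)
- scheduled post-baseline urinalysis visits: 3, at weeks 12, 24 and 48 (Protocol 1.3)
- number of qualitative parameters, k: not stated in either document, so an assumption

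Results per qualitative parameter = participants x visits = 38 x 3 = 114.

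| Assumed k | Post-baseline results at most |
|---|---|
| 2 (nitrite, leukocyte esterase) | 114 x 2 = 228 |
| 8 (all but specific gravity and pH) | 114 x 8 = 912 |

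These are maxima. They assume that all 38 attend every visit and they include any results that also reach an AE table. They measure how much data the rule could touch; they are not an effect on any estimate.

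**Does the endpoint definition matter?** Protocol Table 3 defines the laboratory part of the primary endpoint as "changes in clinically significant laboratory test results (per investigator judgment), vital signs, and ECG results". Protocol 9.3.2 restates it without the limit, as "changes in laboratory test results, vital signs, and ECG results". Under the Table 3 wording, a result not judged clinically significant lies outside the endpoint. Under the 9.3.2 wording it could lie inside. On either reading the mismatch between a listing and the protocol's summary rules remains.

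**The case against.** The strongest reply is that the protocol promises no urinalysis frequency table. Section 9.3.1 says what summaries contain, not that every categorical variable must have one. The laboratory endpoint is summarised through the continuous, toxicity, abnormality and AE tables. Section 9 leaves technical detail to the SAP, which in turn refers to output templates that are not in the documents. The text of SAP 3.4 runs into the next heading, so a missing entry there is weak evidence. The study is single-arm, small and has no hypothesis.

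Much of this stands, and it limits the point to a minor one. It does not remove it: the listing-only sentence is a stated rule, not an omission that a template would fill, and Section 9.3.2 applies descriptive summaries to the safety endpoints other than AEs.

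A reader might infer three stronger things, and the documents support none of them.
- That dipstick findings are never counted. Clinically significant ones reach the TEAE tables, and any item supplied with High/Low/Normal is cross-tabulated.
- That the untabulated values are primary-endpoint results. Table 3, SAP 2 and SAP 14 restrict the laboratory component to clinically significant results. Only the shorter restatements, in the synopsis and Protocol 9.3.2, omit the restriction.
- That an infection signal would be lost. A urinary infection reported as an AE falls under the MedDRA class for infections, is an AESI whether or not it is serious (Protocol 8.4.6; SAP 14.1), and if treatment-emergent is counted as such. A positive leukocyte esterase or nitrite result without a diagnosed infection is much weaker evidence.

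**Conclusion.** The point holds in a limited form. SAP 14.2 departs from the protocol's rules for summarising categorical and safety data, and its visible text does not declare the departure. The consequence is confined to qualitative urinalysis results that are neither recorded as AEs nor classified High/Low/Normal; these receive no count and no shift from baseline.

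The size depends on how the central laboratory reports urinalysis, which neither document states: at most 228 post-baseline results if two parameters are qualitative and 912 if eight are, before dropout. No primary conclusion has been shown to change. This is a low-priority correction, worth making because it is cheap and puts qualitative laboratory results on the same footing as continuous ones.

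**What to change.** Replace the listing-only sentence in SAP 14.2 with text such as: Qualitative urinalysis parameters will be summarised for the SAF by number and percentage in each category at each analysis visit, and as a shift from baseline (normal or abnormal, using the central laboratory's reference category) at weeks 12, 24 and 48 and at the worst post-baseline result; all results will also be listed.

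State in the same place which urinalysis parameters are treated as qualitative and which receive High/Low/Normal. This also settles what counts as an abnormality for the existing abnormality listing. If the sponsor prefers listing only, SAP 3.4 should declare and justify it.

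The cost is a short edit to SAP 14.2 and one table. Urinalysis is already scheduled at baseline and at all three later visits, so no new data are needed. The downside is one more table in which most cells will probably be small or empty.

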### 14.2.1. Laboratory Specific Derivations

All datapoints obtained after informed consent up to database cutoff will be considered. The following abnormality categories will be defined:

- Low: value < lower limit of normal range
- Normal: lower limit of normal range  $\leq$  value  $\leq$  upper limit of normal range
- High: value > upper limit of normal range
  - Notes:
  - Classification will be done in standardized units, using non imputed values and limits.
  - For the worst-case analysis visits, as defined in section 6.4, an additional category low + high is defined in case there are both low and high post-baseline values.

Toxicity grades will be computed according to the National Cancer Institute (NCI) common toxicity criteria for adverse events (CTCAE) toxicity grading list (version 5.0). The implementation of these toxicity grades for analysis

BIOSdata\argenx\Efgartigimod\HAB40220\Biostatistics\Documentation\SAP Document:

1.0 Author: Version Number:

> Version Date: 03 June 2024

Template No.: CS\_TP\_BS016 Revision 7 Reference: CS\_WI\_BS005

Page 34 of 54

is presented in appendix 2. Only the parameters described in appendix 2 will be computed, according to the declared limits for each grade.

Only lab parameters specified within the protocol will be analyzed and, only those both in the protocol and in appendix 2 will be considered for toxicity, all others that are in the protocol and not in appendix 2 but have High/Low/Normal will be presented in the abnormality table.

### 14.3. ECG Evaluations

Results from the central ECG (Electrocardiogram) Reading Centre will be included in the reporting of this study. Single 12-lead ECG(s) will be obtained using an ECG machine. The following ECG parameters will be reported for this study:

- HR (bpm)
- PR Interval (msec)
- QRS Interval (msec)
- RR Interval (msec)
- QT Interval (msec)
- QTcF Interval (msec)
- QTcB Interval (msec)

All datapoints obtained after informed consent up to database cutoff will be considered.

The following summaries will be provided for ECG data:

ECG parameters will be summarized using descriptive statistics at each analysis visit for the SAF for FPA only.

Abnormalities of the actual values will be presented as cross-tabulations of the abnormality at each postbaseline analysis visit and at the worst-case analysis visit versus the baseline abnormality. Numbers and cumulative numbers (QTc only) of participants with treatment-emergent abnormalities will also be shown. The denominator for the percentage is the total number of participants per treatment arm and per analysis visit in the SAF for FPA only.

Abnormalities of the QTc changes will be presented as tabulations of the change abnormality at each postbaseline analysis visit and at the worst-case analysis visit. Cumulative numbers of participants with change abnormalities will also be shown. The denominator for the percentage is the total number of participants per treatment arm and per analysis visit in the SAF. Produced for the FPA only.

All ECG data will be listed, but only for participants with any postbaseline abnormality.

### 14.3.1. ECG Abnormal Criteria

Abnormal quantitative ECG measurements will be identified in accordance with the following predefined abnormal criteria for HR, QRS and PR interval:

	HR (bpm)	PR (ms)	QRS (ms)
Low	<40	<120	-

Document: BIOSdata\argenx\Efgartigimod\HAB40220\Biostatistics\Documentation\SAP

Author: Version Number: 1.0

Version Date: 03 June 2024

Template No.: CS TP BS016 Revision 7 Reference: CS WI BS005

Page 35 of 54

Normal	40-100	120-220	0-120
High	>100	>220	>120

Note: For the worst-case analysis visit, as defined in Section 6.4, an additional category "low + high" is defined if there are both low and high postbaseline values.

Absolute values for QT interval, QTcB interval and QTcF will be classified as:

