# 2.2. Background

The novel SARS-CoV-2 and resulting COVID-19 emerged in late 2019, becoming an ongoing global pandemic in 2022. Because of COVID-19, many patients develop chronic, debilitating symptoms after recovery from the acute infection. Multiple terms have been used to describe the constellation of symptoms, including long-COVID, long-haul COVID, and post-acute sequelae of SARS-CoV-2 syndrome. Typical symptoms of long-COVID include breathlessness, fatigue, cognitive impairment (eg, brain fog), orthostatic intolerance, and palpitations. These symptoms are often debilitating, and most patients receive disability or modified independence. Evidence is emerging that autonomic dysfunction underlies the symptoms that persist after the acute SARS-CoV-2 infection resolves.

POTS in patients who continue to have long-lasting symptoms after recovery from the initial SARS-CoV-2 infection has been identified in several case reports.  $^{5,6}$  A POTS diagnosis is based on evaluations for excessive orthostatic tachycardia (sustained HR increment of  $\geq$ 30 bpm within 10 minutes of standing or head-up tilt  $\geq$ 40 bpm in 12 to 19 years old); absence of orthostatic hypotension; frequent symptoms of orthostatic intolerance during standing; duration of symptoms for  $\geq$ 3 months; and absence of other conditions explaining sinus tachycardia. Patients who develop POTS after COVID-19 are designated in this study as having PC-POTS.

Currently, the underlying pathophysiology and effective treatments are unknown for PC-POTS. Pharmacologic therapy mainly focuses on orthostatic symptoms, targeting blood volume expansion and stabilizing HR and blood pressure; however, POTS may be related to immune dysfunction and autoimmunity preceded by infection. Several infectious pathogens may be associated with the development of POTS, including SARS-CoV-2. 8,9,10 Patients with POTS

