## LIST OF ABBREVIATIONS

Abbreviation	Term
ADA	antidrug antibody(ies)
AE	adverse events
AESI	adverse events of special interest
BLQ	below the limit of quantification
bpm	beats per minute
CI	confidence interval
COMPASS 31	Composite Autonomic Symptom Score
eCRF	Electronic case report form
CTCAE	Common Terminology Criteria for Adverse Events
CV	Coefficient of variation
DBP	diastolic blood pressure
ECG	electrocardiogram
EDV	early discontinuation visit
ENR	Enrolled Analysis Set
EoS	end of study
ЕоТ	end of treatment
FAS	full analysis set
FPA	Final Planned Analysis
IA	Interim Analysis

Document: BIOSdata\argenx\Efgartigimod\HAB40220\Biostatistics\Documentation\SAP

Author: Version Number: 1.0

Version Date: 03 June 2024

Template No.: CS\_TP\_BS016 Revision 7 Reference: CS\_WI\_BS005

Page 9 of 54

ICF	informed consent form
IgG	immunoglobulin G
IMP	investigational medicinal product
IRR	Infusion/injection related reactions
LLN	lower limit of normal
MaPS	Malmö POTS symptom score
MedDRA	Medical Dictionary for Regulatory Activities
msec	millisecond
NCI	National Cancer Institute
ND	not determined
OLE	open-label extension
PD	pharmacodynamic(s)
PGI-C	Patient Global Impression - Change
PGI-S	Patient Global Impression - Severity
PK	pharmacokinetic(s)
PKAS	pharmacokinetic analysis set
POTS	postural orthostatic tachycardia syndrome
PROMIS	Patient-Reported Outcomes Measurement Information System
PT	preferred term
QTc	corrected QT interval
QTcB	Bazett's corrected QT interval
QTcF	Fridericia's corrected QT interval
Q2W	Every 2 weeks
QW	Once weekly
~ ··	l l

Document: BIOSdata\argenx\Efgartigimod\HAB40220\Biostatistics\Documentation\SAP

Author: Version Number: 1.0

Version Date: 03 June 2024

Template No.: CS\_TP\_BS016 Revision 7 Reference: CS\_WI\_BS005

Page 10 of 54

SAE	serious adverse event
SAP	statistical analysis plan
SAF	safety analysis set
SBP	systolic blood pressure
SD	standard deviation
SE	standard error
SFV	safety follow-up visit
SOC	system organ class
TEAE	treatment-emergent adverse event
ULN	upper limit of normal
ULQ	upper limit of quantification
WOCBP	women of childbearing potential

Document: BIOSdata\argenx\Efgartigimod\HAB40220\Biostatistics\Documentation\SAP

Author: Version Number: 1.0

Version Date: 03 June 2024

Template No.: CS\_TP\_BS016 Revision 7 Reference: CS\_WI\_BS005

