## 6.5. Treatment-emergent Abnormality/Toxicity

A treatment-emergent abnormality/toxicity (for laboratory assessments, vital signs, or ECGs) is defined as any

Document: BIOSdata\argenx\Efgartigimod\HAB40220\Biostatistics\Documentation\SAP

1.0 Author: Version Number:

> Version Date: 03 June 2024

Template No.: CS\_TP\_BS016 Revision 7 Reference: CS\_WI\_BS005

<sup>b Post baseline visit Day 1.

Page 23 of 54

postbaseline abnormality/toxicity that was not present at baseline (eg, hemoglobin normal at baseline and grade 1 postbaseline; glucose low at baseline and high postbaseline; QTcF [450; 480] ms at baseline and >500 ms postbaseline).

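### SAP 14.3.1 classifies uncorrected QT with the same 450/480/500 ms limits as QTcB and QTcF and names no governing correction, so the ECG category tables can mislabel tracings and contradict each other

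*SAP*

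**What the plan says.** SAP 14.3 reports heart rate, PR, QRS, RR, QT, QTcF and QTcB. SAP 14.3.1 then states: "Absolute values for QT interval, QTcB interval and QTcF will be classified as" at or below 450 ms (normal), 450 to 480, 480 to 500, and above 500 ms. It sets no heart-rate condition and no separate limits for uncorrected QT. Change from baseline is classed as at or below 30 ms (normal), 30 to 60, and above 60 ms. The worst case is the highest postbaseline value and its associated change.

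SAP 14.3 cross-tabulates the actual-value classes against baseline at each visit and at the worst case. It adds: "Numbers and cumulative numbers (QTc only) of participants with treatment-emergent abnormalities will also be shown". For change it says: "Abnormalities of the QTc changes will be presented as tabulations of the change abnormality at each postbaseline analysis visit", again with the worst case. So the change classes and cumulative counts cover QTcB and QTcF. Raw QT remains in the actual-value cross-tabulation and, on the natural reading, in the non-cumulative treatment-emergent counts.

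No governing correction is named. The nearest thing is an illustration in SAP 6.5, which takes QTcF between 450 and 480 "ms at baseline and >500 ms postbaseline" as an example of a treatment-emergent abnormality.

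ECG results belong to the primary endpoint (Protocol section 3, Table 3; SAP 14).

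**The concern.** The 450/480/500 ms limits suit a rate-corrected interval. Raw QT falls as heart rate rises even when repolarisation is unchanged, so one fixed limit means different things at different rates. QTcB has a milder form of the same problem relative to QTcF: it exceeds QTcF at any rate above 60 bpm, by a margin that grows with rate.

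This matters more here than in most trials. Protocol 2.2 says: "A POTS diagnosis is based on evaluations for excessive orthostatic tachycardia". Tachycardia is also among the symptoms scored by MaPS, a secondary efficacy endpoint. Heart rate may therefore differ between participants and between visits. If three intervals share one set of classes and none is designated in advance, the same participant can be normal in one table and abnormal in another, with no stated rule for which to believe. About 38 participants are expected, so one spurious entry moves an overall percentage by up to 1/38 = 2.6 points.

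**Working it through.** **Inputs.** The limits are those of SAP 14.3.1. The SAP abbreviation list glosses QTcF as "Fridericia's corrected QT interval" and QTcB as Bazett's correction. The SAP does not print the formulas, so I used the standard ones. Heart rate (HR) at the ECG is not given and is varied as an assumption. QTcF is taken as the reference. The plan has no figure of its own to reproduce.

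**Formulas.** RR = 60/HR in seconds; QTcF = QT / RR^(1/3); QTcB = QT / RR^(1/2). Hence QTcB = QTcF × RR^(−1/6).

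**1. Raw QT at the top of the normal class (450 ms).**

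| HR (bpm) | RR (s) | QTcF (ms) |
|---|---|---|
| 50 | 1.200 | 424 |
| 60 | 1.000 | 450 |
| 70 | 0.857 | 474 |
| 80 | 0.750 | 450 / 0.750^(1/3) = 495 |
| 90 | 0.667 | 515 |
| 100 | 0.600 | 450 / 0.600^(1/3) = 534 |

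Turned round, a given QTcF reads as normal on raw QT once HR ≥ 60 / (450/QTcF)^3:

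- QTcF 480: 60 / 0.9375^3 = 72.8 bpm
- QTcF 500: 60 / 0.900^3 = 82.3 bpm
- QTcF 520: 92.6 bpm

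All three rates lie inside the SAP's own normal ECG heart-rate range of 40 to 100 bpm. Below 60 bpm the error reverses: a raw QT just above 450 ms is flagged at 50 bpm although QTcF is only about 424 ms.

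**2. QTcB actual values.** QTcF 420 at 100 bpm gives 420 × 0.600^(−1/6) = 457 ms, in the 450 to 480 class, while QTcF is normal. QTcB passes 450 ms when HR > 60 × (450/QTcF)^6:

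- QTcF 430: 78.8 bpm
- QTcF 420: 90.8 bpm
- QTcF 410: 104.9 bpm
- QTcF 400: 121.6 bpm

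**3. QTcB change with QTcF constant at 420 ms.**

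| HR change (bpm) | QTcB change (ms) | Change class |
|---|---|---|
| 60 to 90 | +29.4 | normal |
| 60 to 95 | +33.4 | 30 to 60 |
| 60 to 100 | 457.3 − 420.0 = +37.3 | 30 to 60 |
| 70 to 100 | +26.4 | normal |
| 100 to 70 | −26.4 | normal |

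Starting from 60 bpm, a rise of about 35 bpm is enough to produce a change abnormality with no change in QTcF.

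**4. Worst case.** Because the highest value is taken, at constant QTcF the raw-QT worst case comes from the slowest tracing and the QTcB worst case from the fastest. Neither choice reflects repolarisation.

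**The case against.** The strongest reply is that nothing is lost. QTcF is classified with the same limits, so a tracing with QTcF 495 or 534 ms that is normal on raw QT still appears in the QTcF table as 480 to 500 or above 500. That stands, and it rules out a reading that a repolarisation signal would go undetected.

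A reader might also infer that a falling heart rate could hide a true increase in the QTcB change table. Take QTcF rising from 410 to 445 ms while heart rate falls from 100 to 75 bpm: QTcB goes from 446.4 to 461.9 ms, only +15.4 ms before rounding, which is normal. But the planned QTcF change table shows +35 ms, and QTcB itself crosses 450 ms, which SAP 6.5 counts as treatment-emergent. One cell misleads; the increase is not hidden. Nor do the documents predict such a fall in heart rate: baseline is the last parent-study value (SAP 6.2), and the parent trial randomised 2:1 to efgartigimod.

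A reader might infer, too, that raw QT distorts every ECG output. SAP 14.3 does not support that, since it confines the change classes and cumulative counts to QTc.

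Heart rate at the ECG is unknown. The tachycardia of POTS is orthostatic, and Protocol 8.3.3 does not give the position for the ECG. So QTcB can flag normal tracings; the documents do not show that it will. For QTcF of 410 ms or less, this needs rates above the SAP's normal range. The raw-QT problem needs only about 73 to 82 bpm.

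Finally, heart rate and RR are already reported, no hypothesis is tested (Protocol 9.1), and ECG summaries are planned for the final analysis only. All of this limits the weight of the point. None of it makes a QTc limit suitable for raw QT, or says which table governs.

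**Conclusion.** The point holds and is minor. Putting uncorrected QT through limits meant for corrected intervals gives wrong labels at ordinary heart rates: QTcF 480 ms is called normal from about 73 bpm and QTcF 500 ms from about 82 bpm. This affects the actual-value cross-tabulation and the non-cumulative treatment-emergent counts. QTcB can disagree with QTcF in actual values (457 against 420 ms at 100 bpm) and in change (+37 against 0 ms for 60 to 100 bpm). With no governing measure stated in advance, the safety tables can contradict each other. How often this would happen cannot be estimated, because the heart rates are an assumption. The result also rests on the standard Bazett and Fridericia formulas and on QTcF as the reference, which is the measure the SAP uses in its own example.

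**What to change.** In SAP 14.3 and 14.3.1:

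- Remove uncorrected QT from the category tables and summarise it descriptively only.
- Name QTcF as the governing measure for the absolute, change-from-baseline, worst-case and treatment-emergent categories.
- Keep the QTcB categories as supplementary output, read with ECG heart rate.

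Applied to the examples above, a QT of 422 ms at 100 bpm would be read at the 500 ms QTcF limit instead of as normal, and a QTcF of 420 ms at 100 bpm would be read as normal.

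The cost is SAP wording and fewer tables. QTcF, heart rate and RR are already reported, so no new data are needed, and the change can be made before the final analysis. The downside is that QTcB categories lose their equal standing and become supplementary.
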